1. INTRODUCTION AND RATIONALE

Anemia due to surgery is often treated with iron therapy to ensure that the hemoglobin will return to a normal value more rapidly. Several studies in orthopaedic and cardiac surgery, in which iron therapy was given postoperatively, show that after 6 to 10 weeks the hemoglobin was not significantly different between patients treated with oral preparations and patients treated with a placebo.¹⁻⁵ Therefore, the scientific evidence for this treatment, especially in case of a moderate anemia (Hb 5.0 – 7.0 mmol/L), is limited.

Annually there are also thousands of patients treated with either oral iron therapy or intravenous iron therapy after a caesarean section. Hospital wide protocols are available for the diagnosis and treatment of postpartum anemia, but not specifically for post caesarean anemia. The reason for giving iron preparations for a postoperative anemia is both patient and doctor-dependent. A patient with a hemoglobin level of 6.5 mmol / L without symptoms is less likely to receive iron supplementation than a patient with a hemoglobin level of 6.5 mmol / L with complaints (eg weakness, fatigue). In addition, one doctor will prescribe iron preparation more easily than another doctor does. In other words, there is no clear national or international guideline for the treatment of post caesarean anemia through iron suppletion. Giving iron supplements to patients can lead to side effects, and because of the fact that it is prescribed very frequently it leads also to high costs for medical care. Given the absence of good evidence, is giving iron post caesarean really necessary? And if so, which patients with a post caesarean anemia should get iron supplementation? Is the intravenous form superior to the oral form? Is measuring the hemoglobin level only enough to start therapy or should other blood values be determined for this decision?

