In a prospective study, Iperen et al. examined the effects of larger and smaller surgery on erythropoiesis, iron metabolism and the acute phase response proteins.²⁰ They found that both major and minor surgery induce a state of hypoferremia despite adequate iron stores. They conclude that giving oral iron in the first weeks after surgery is not effective (if iron stores are normal before surgery). Also Cutress et al. drew this conclusion after examining the importance of oral iron therapy in patients undergoing surgery for breast cancer.²¹ They concluded that because of the operation and the associated inflammatory response a disturbance occurs in the serum iron indices which may lead to inadequate supply of iron to the bone marrow and thus a disturbance in the red blood cell synthesis. This phenomenon does not appear to be related to the amount of bloodloss but to the inflammatory response, causing a blockage of iron mobilization. That's why no effect is to be expected of giving postoperative oral iron. Giving intravenous iron circumvents this problem.

Bisbe et al. compared ferric carboxymaltose with ferrous oral glycine sulphate for postoperative anaemia after total knee arthroplasty. They found that postoperative IV ferric carboxymaltose provided significant benefit over oral ferrous glycine sulphate, particularly in patients with preoperative iron deficiency, severe postoperative anemia, or both.²²

As mentioned earlier, in Dutch hospitals oral and intravenous iron preparations are often prescribed for post caesarean patients with moderately low hemoglobin levels, although

this is not scientifically well-fetched. The purpose of this randomized controlled trial is to get an answer to these questions in patients with post caesarean anemia.

1. What is the effect of oral iron therapy on hemoglobin levels in the first weeks postoperatively?
2. What is the effect of intravenous iron therapy on hemoglobin level in the first weeks postoperatively?
3. What is the effect of oral iron therapy on quality of life in the first weeks postoperatively?
4. What is the effect of intravenous iron therapy on quality of life function in the first weeks postoperatively?

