In addition, some of the iron-metabolism related parameters that may be of value in predicting the effect of iron supplementation will be determined (transferrin, CRP, ferritin, hepcidin). It will also be taken into consideration whether or not this is proportionate to the side effects of medication including the inconvenience of taking medication, and the associated costs.

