2. OBJECTIVES

Primary objective:

Comparison of the hemoglobin level 3 and 6 weeks postoperatively between the different groups

Secondary objectives:

- Comparison of quality of life after 1, 3 and 6 weeks postoperatively between the different groups
- Comparison of the side-effects of various drugs
- Is there a “subgroup” of patients who have the greatest effect of the medication used (eg patients with low ferritin)
- Is there a “subgroup” of patients who respond better to ferinject than ferrous fumarate and vice versa (eg patients with elevated CRP).
- What are the costs of taking oral iron or intravenous iron

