7.1.2 Secondary study parameters

- Quality of life after 1, 3 and 6 weeks
- Side effects of medication
- Predictive value of other parameters such as CRP, transferrin, ferritin and hepcidin
- Cost analysis

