7.2 Randomization, blinding and treatment allocation

Randomisation is performed by the ALEA Screening and Enrollment Application Software of Formsmvision BV (Abcoude). Minimisation with stratification factor Hemoglobin (5.0-6.0 or 6.1-7.0), age (<60 years or >=60 years), ASA (1-2 or 3-5), type of surgery (laprotomic, laproscopic or vaginal and other) and amount of blood loss (<500 mL or >=500 mL) will be performed. The minimization method supported by ALEA is based on the minimization principles published in a paper by Pocock & Simon²³.

With the kit-number the pharmacy knows which package the patient should receive. It will be ensured that the infusion line and the flask with NaCl or Ferinject[®] will be packed. Also the venflon will be covered by a gauze. The placebo capsules will exactly resemble the capsulated ferrous fumarate tablets.

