9.4 Secondary study parameters

Quality of life

Each patient will be asked to complete three questionnaires at four times: at baseline after informed consent before starting iron treatment, and 1, 3 and 6 weeks postoperatively. The questionnaires are: 1) the EuroQoL, a generic health related quality of life questionnaire. In this questionnaire patients indicate their current health in five dimensions: mobility, self-care, usual activities, pain/discomfort, and anxiety/depression 2) the Multi-Dimensional Fatigue Questionnaire which is a 20-item self-reported instrument to measure fatigue. At baseline (first day postoperatively in the hospital but before the study-medication is started) patients will be asked to complete the questionnaires. At 1 week after start of the treatment, the research nurse will call the patient at home to ask whether the second questionnaire has been completed. After 3 weeks the nurse visits the patient and will ensure that the questionnaires about the quality of life after 1 and 3 weeks are completed. At 6 weeks, the patient will visit the outpatient clinic and will also be seen by the research nurse who will check whether the last questionnaire has also been completed.

Quality of life data between the groups will be analysed using Repeated Measurement

ANOVA.

Side effects of the medication

The next side effects will be registered: headache, constipation, diarrhea, nausea, dizziness, rash and stomach-ache. On questionnaire B, C, and D the patients can indicate whether there is any of these side effects.

For each potential side effect, the percentage of patients reporting it will be compared between groups. Groups will be compared using the Chi-square test.

Predictive value of other parameters

We will determine for number of parameters whether they predict patients' sensitivity to iron supplementation. These parameters are: CRP, transferrin, ferritin and hepcidin. The significance of these parameters will be determined by doing subgroup analyses among patients with either high or low values of the parameters (i.e. the similar analyses as in 9.1 but within subgroups).

Cost-analysis

Resource use and costs of the intravenous and oral iron therapy will be measured. If relevant and appropriate, a cost-minimisation or a cost-effectiveness analysis will be performed. In that case, the analysis will include a time-horizon of 6 weeks and be performed from a health care perspective.

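### As planned, section 9.4 does not examine post-operative hemoglobin as a modifier of the iron effect, nor judge the four markers over and above it

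*Combined protocol and SAP*

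**What the plan says.** Section 1 asks which women should receive iron, and adds: "Is measuring the hemoglobin level only enough to start therapy or should other blood values be determined for this decision". It describes current prescribing as resting on hemoglobin, complaints and the individual doctor. It cites a knee-replacement trial in which intravenous iron did better than oral iron, "particularly in patients with preoperative iron deficiency, severe postoperative anemia, or both". It closes by saying that "some of the iron-metabolism related parameters that may be of value in predicting the effect of iron supplementation will be determined".

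Section 2 makes it a secondary objective to find a subgroup "of patients who have the greatest effect of the medication used (eg patients with low ferritin". Section 7.1.2 uses an open list: "Predictive value of other parameters such as CRP, transferrin, ferritin and hepcidin". Section 9.4 then closes it: "These parameters are: CRP, transferrin, ferritin and hepcidin". The method is "doing subgroup analyses among patients with either high or low values of the parameters", repeating the analyses of 9.1, which are t-tests on change in hemoglobin.

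Post-operative hemoglobin before treatment has other uses. It is the entry criterion (4.2) and a minimisation factor (7.2: "Minimisation with stratification factor Hemoglobin (5.0-6.0 or 6.1-7.0"). Baseline hemoglobin is also the starting value of the change score (9.1) and part of a descriptive comparison of the arms (9.2). Regression replaces the t-test only if the arms differ at baseline (9.2, 9.3).

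**The concern.** No section asks whether the iron effect differs between a woman near 5 and a woman near 7 mmol/L, and none asks what a marker adds once her hemoglobin is known. Yet hemoglobin is the value clinicians already have. The cited knee-surgery result points to severity of anemia as well as iron deficiency, and of the two 9.4 follows up only iron status.

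The second consequence is misattribution. If the iron effect depends on hemoglobin, and a marker is correlated with hemoglobin, then the high and low halves of that marker differ in hemoglobin. They will then differ in treatment effect even if the marker has no effect of its own. The regression in 9.3 does not guard against this: it is triggered by imbalance between arms, not between marker-high and marker-low women. At stake is a wrong conclusion about which extra blood tests help to select patients.

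**Working it through.** **1. The plan's own figure.** Section 4.4 gives a difference of 0.5, SD 0.7, alpha 5% (two-sided by 9.5) and power 80%. n per group = 2 × (0.7/0.5)² × (1.960 + 0.842)² = 30.8, so 31. The exact t-test gives 31.76, so 32, with power 80.3%. Then 3 × 32 = 96 and 96/0.80 = 120. The figures reproduce, and the checks below use 32 to 40 women per arm.

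**2. Assumed inputs for the carry-over.** The documents give neither the marker-hemoglobin correlation r nor the slope of the iron effect on hemoglobin. I take r = 0.3, 0.5, 0.7 and a fall in effect of 0.3 to 0.5 mmol/L per 1 mmol/L higher hemoglobin. The spread of hemoglobin within 5-7 is not given either. A normal distribution with SD 0.7, placed so that 31/46 = 67% lies within 5-7 (the counts in 4.4) and then truncated, has SD 0.455, taken as 0.46. Section 4.4 does not say that 0.7 describes day-1 hemoglobin, so this too is an assumption.

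**3. Carry-over with a median split of the marker.** Hemoglobin gap between halves = 2 × √(2/π) × r × 0.46. Spurious difference in effect = gap × slope.

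| r | Gap (mmol/L) | Slope 0.3 | Slope 0.5 |
|---|---|---|---|
| 0.3 | 0.22 | 0.07 | 0.11 |
| 0.5 | 0.37 | 0.11 | 0.18 |
| 0.7 | 0.51 | 0.15 | 0.26 |

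Cross-check by another route: if the effect differs by 0.5 mmol/L between hemoglobin halves, the share carried over is (2/π) × arcsin(r) = 19%, 33%, 49%. That is 0.10, 0.17 and 0.25 mmol/L.

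**4. How often this would mislead a formal test.** With m women per arm in each marker half, the SE of the difference in effects is 0.7 × √(4/m): 0.35 for m = 16 and 0.31 for m = 20. A spurious 0.07 raises the 5% rejection rate of an interaction test to about 5.5%. A spurious 0.26 raises it to about 12% (m = 16) or 13% (m = 20).

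**5. What an added hemoglobin analysis could show.**
- Two equal strata, 16 to 20 per arm in each: power for a 0.5 mmol/L interaction is 30% to 36%, and the interaction detectable with 80% power is 0.98 to 0.88 mmol/L.
- If the smaller stratum holds only 25% of 96 evaluable women, power for 0.5 falls to 23%.
- Eighty per cent power for 0.5 needs 4 × (0.7 × 2.802/0.5)² = 61.5, so 62 per cell, or 6 × 62 = 372 women.
- Hemoglobin as continuous, 40 per arm: SE of the slope difference = (0.7/0.46) × √(2/40) = 0.34, a 95% half-width of 0.67 per 1 mmol/L. Power for a slope of 0.3 to 0.5 is about 14% to 31%.

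**6. Price of judging marker and hemoglobin together.** The SE of the marker interaction grows by roughly 1/√(1 − r²): 1.05, 1.15 and 1.40 for r = 0.3, 0.5, 0.7.

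**The case against.** The question about hemoglobin alone is posed in the background. It is not among the four numbered research questions in section 1 or the objectives in section 2. The closing part of section 1 confines the marker work to iron metabolism, and 9.4 is headed as concerning other parameters, presumably other than hemoglobin. This stands: 9.4 does not fail a listed objective. Still, the subgroup objective is worded openly, and advice on which marker to measure is of little use without reference to the hemoglobin already known.

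A reader might infer that the trial cannot answer the question at all. The documents do not support that. Every woman enters on hemoglobin 5-7 with no criterion on the four markers, so the comparisons with placebo already test treating on that range alone. Hemoglobin is also measured in everyone and minimised on. What is missing is the gradient inside the range and the adjusted marker effect, and both can be added to the analysis.

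A reader might also infer that a marker which tracks hemoglobin will look predictive. Step 4 shows otherwise: even the extreme corner lifts a 5% interaction test only to about 13%. Section 1 also reports a study that tied the post-operative iron disturbance to inflammation and not to the amount of blood lost, which may point to weak correlations.

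The knee-surgery citation is limited support. It compared intravenous with oral iron in another population, severe anemia is not defined here, and women below 5 mmol/L are excluded (12.2).

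Finally, the added analysis is weak: its half-width of 0.67 exceeds the slopes assumed. That is true, but the four listed marker subgroups share the weakness, so it is a reason to label the results exploratory and not a reason to leave out hemoglobin.

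**Conclusion.** The point holds as a gap in the analysis plan, not in the design. Section 9.4 neither tests post-operative hemoglobin as an effect modifier nor judges the markers over and above it, so it does not address the rationale's question within 5-7 mmol/L. A correlated marker could take some credit for a hemoglobin effect. The 0.07-0.26 mmol/L range depends entirely on the assumed correlations, slopes and SD of 0.46. Only the top of it, with r = 0.7 and slope 0.5 together, reaches half of the 0.5 mmol/L design difference. The primary comparison and safety are untouched. The change is worth making because it costs little and sets down the analysis before the data are seen.

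**What to change.** In 9.4:
- Add an exploratory interaction of treatment with post-operative, pre-treatment hemoglobin. Fit hemoglobin as continuous, with its main effect in the model, and display the effects for the minimised strata 5.0-6.0 and 6.1-7.0.
- Replace the separate subgroup t-tests for CRP, transferrin, ferritin and hepcidin by a treatment-by-marker interaction, each in a model that also contains the treatment-by-hemoglobin term. Report what the marker adds.
- Give estimates with 95% confidence intervals and label all of it exploratory.
- State the low power: about 30-36% for a 0.5 mmol/L interaction with equal strata, and a half-width of about 0.67 per 1 mmol/L at 40 per arm if the hemoglobin SD is 0.46.

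The cost is SAP wording and a few model terms, with no new data or visits. Adjusted marker estimates will be less precise if the correlation is high (step 6). The number of tests need not grow: 4 markers × 2 halves × 3 contrasts × 2 time points is 48 t-tests, while 5 interactions × 3 contrasts × 2 time points is 30.

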9. STATISTICAL ANALYSIS

9.1 Primary study parameter

Primary study parameter is change in hemoglobin level (mmol/L) between baseline and either 3 or 6 weeks postoperatively. Differences in change between the two experimental groups, and between each experimental group and the control group will be tested by use of the Student's T-test.

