9.3 Multivariable analysis

In case of prognostically important baseline differences between groups, multivariable linear regression analysis will be carried out instead of the Student's T-test.

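### Section 9.4 judges whether a marker predicts response to iron by t-tests inside high and low subgroups and never tests whether the treatment effect differs between them

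*Combined protocol and SAP*

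**What the plan says.** Section 2 has two secondary objectives about subgroups. One looks for "patients who have the greatest effect of the medication used (eg patients with low ferritin"). The other looks for "patients who respond better to ferinject than ferrous fumarate and vice versa (eg patients with elevated CRP"). Section 9.4 puts the question as "whether they predict patients' sensitivity to iron supplementation", for CRP, transferrin, ferritin and hepcidin.

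The method follows in section 9.4: "The significance of these parameters will be determined by doing subgroup analyses among patients with either high or low values of the parameters". A parenthesis explains it: "i.e. the similar analyses as in 9.1 but within subgroups". Section 9.1 is a set of Student's t-tests on change in hemoglobin at 3 or 6 weeks: "Differences in change between the two experimental groups, and between each experimental group and the control group will be tested".

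The only regression in the plan is in section 9.3, and it serves another purpose: "In case of prognostically important baseline differences between groups, multivariable linear regression analysis will be carried out". It contains no treatment-by-marker term. Where the protocol uses the word interaction, in section 12.1, it means drug interactions.

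Section 9.4 gives no cut-off or scale for high and low. Annex 1 schedules the markers both pre-operatively and on day 1, before treatment, and section 9.4 does not say which sample defines the subgroup.

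**The concern.** Predicting sensitivity to iron, and finding where the effect is greatest, are questions about a difference between two treatment effects. The planned tests give a separate p-value in each subgroup and stop there. One p-value below 0.05 and another above it is not evidence that the effects differ. With small subgroups that pattern is common when the effects are identical.

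Two of the five secondary objectives depend on this analysis, and the introduction asks whether blood values other than hemoglobin should guide the decision to treat. A marker could be put forward for that role only because one small subgroup crossed the threshold and the other did not.

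The undefined inputs add to the problem. The introduction reports a cited study in breast cancer surgery as concluding that "because of the operation and the associated inflammatory response a disturbance occurs in the serum iron indices". That is not evidence from this population, but it is a reason to expect that pre-operative and day-1 values could classify patients differently. If the sample and the cut-off stay open, both could be chosen after the results are seen.

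**Working it through.** **Inputs from the plan.** Effect 0.5 mmol/L, SD 0.7 mmol/L, 32 per arm, 96 in total, raised to 120 (section 4.4), so 40 per arm if equal; two-sided alpha 5% (section 9.5); dropout 10-20% (section 7.5); 4 markers (section 9.4); 3 contrasts and 2 time points (section 9.1).

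**Assumptions not in the plan.** A marker is read as predictive when exactly one of its two subgroups has p < 0.05. One contrast at one time point is considered. SD 0.7 applies to the change in hemoglobin. The split is 50/50 or 25/75.

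**Step 1: the plan's own figure.** Normal approximation: n = 2 × (1.96 + 0.8416)² × (0.7/0.5)² = 30.8, so 31. The exact t-test has power 0.790 at 31 and 0.803 at 32, so 32 per arm reproduces. 96/(1 − 0.20) = 120 also reproduces.

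**Step 2: power inside a subgroup.** Noncentral t with noncentrality (0.5/0.7) × √(n/2); for n = 16 this is 2.02.

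| Patients per arm in the subgroup | 8 | 10 | 16 | 20 | 24 | 30 |
|---|---|---|---|---|---|---|
| Power | 0.265 | 0.327 | 0.498 | 0.595 | 0.678 | 0.776 |

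**Step 3: non-predictive marker, true effect 0.5 in both subgroups.** With subgroup powers p and q, exactly one is significant with probability p(1 − q) + q(1 − p).

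| Subgroups (patients per arm) | SD 0.7 | SD 0.5 |
|---|---|---|
| 16 and 16 | 0.498 × 0.502 × 2 = 0.500 | 0.342 |
| 20 and 20 | 0.595 × 0.405 × 2 = 0.482 | 0.228 |
| 8 and 24 | 0.265 × 0.322 + 0.678 × 0.735 = 0.584 | 0.533 |
| 10 and 30 | 0.327 × 0.224 + 0.776 × 0.673 = 0.595 | 0.442 |

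**Step 4: other true effects, SD 0.7.**

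| True effect (mmol/L) | 0 | 0.25 | 0.5 | 0.75 | 1.0 |
|---|---|---|---|---|---|
| 16 and 16 | 0.095 | 0.275 | 0.500 | 0.276 | 0.050 |
| 8 and 24 | 0.095 | 0.283 | 0.584 | 0.487 | 0.244 |

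**Step 5: truly predictive marker, 0.5 in one half and 0 in the other.** With 16 per arm in each half: 0.498 × 0.95 + 0.05 × 0.502 = 0.498. With 20: 0.595 × 0.95 + 0.05 × 0.405 = 0.586. At 32 per arm the pattern is therefore as frequent for a useless marker (0.500) as for a useful one (0.498).

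**Step 6: the interaction test.** In simulations of the model proposed below (3,000 trials per scenario, non-predictive marker, IV effect 0 or 0.5, equal variances), the rejection rate per contrast was 0.044 to 0.054 with a split marker, 0.043 to 0.047 with a continuous normal marker and 0.052 to 0.058 with a skewed one.

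For power, SE = 0.7 × √(2/a + 2/b), where a and b are the patients per arm in the two subgroups.

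| Subgroups (patients per arm) | SE | Power for a 0.5 difference in effect | Difference detectable with 80% power |
|---|---|---|---|
| 16 and 16 | 0.350 | 0.29 | about 1.0 |
| 20 and 20 | 0.313 | 0.35 | about 0.9 |
| 8 and 24 | 0.404 | 0.23 | about 1.15 |
| 10 and 30 | 0.361 | 0.28 | about 1.0 |

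**Step 7: number of tests.** As written: 4 markers × 2 subgroups × 3 contrasts × 2 time points = 48 t-tests, so 48 × 0.05 = 2.4 expected false positives if iron has no effect anywhere. Interaction tests would number 4 × 3 × 2 = 24, with 24 × 0.05 = 1.2 expected.

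**The case against.** The strongest reply is that the decision rule is not the plan's. Section 9.4 does not say that a marker counts as predictive when exactly one subgroup is significant, and the frequency of that pattern runs from 5% to 60% over the cases shown, with the headline near the top. This is fair, and the figures are an illustration only. The mismatch between question and method does not depend on them: section 9.4 states no other way to reach a conclusion about a marker.

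Second, the within-subgroup IV versus oral test does bear on the second objective. An interaction alone could be significant although IV beats oral in both subgroups. This stands in part, so the within-subgroup estimates should still be reported. They cannot show that the comparison changes with marker level.

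Third, the 5% error rate of the interaction test is not guaranteed. With an 8/24 split and SDs of 0.9 in the small subgroup and 0.6 in the large one, a pooled-variance test rejects in about 11% of trials; with a 16/16 split it stays at about 5%. The rate therefore holds only when variances are similar or the split is even. Even 11% is far below 58%.

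Fourth, 24 interaction tests carry their own multiplicity, and power is low. Both are true. They are reasons for an exploratory label and confidence intervals, not for keeping a test of a different question.

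Finally, the missing cut-off and sample time would be gaps under either method. That is also true, but the same edit can close them.

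**Conclusion.** The concern holds. Followed as written, section 9.4 tests whether iron works inside each marker subgroup, while section 2 and section 9.4 itself ask whether the effect differs between them. No other part of the plan supplies that comparison.

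Under the one-subgroup-only reading, with a true effect of 0.5 mmol/L and SD 0.7, a non-predictive marker looks predictive in 48% to 60% of trials per contrast and time point. With SD 0.5 this falls to 23% to 53%. With SD 0.7 and equal halves at 32 per arm it is 9.5% at zero effect and 5% at 1.0 mmol/L. These figures rest on the assumed reading rule, the assumed splits and a common SD for change.

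The consequence is confined to secondary objectives. The plan should be changed, but the primary comparison does not depend on it.

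**What to change.** Replace the sentence in section 9.4 that sets the subgroup method with:

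> For each marker, one linear regression in all randomised patients is fitted to the hemoglobin outcome of 9.1 (change from baseline, at the 9.1 time points), with treatment (three arms), baseline hemoglobin (the value used to compute the change in 9.1), the marker and the treatment-by-marker interaction. Missing outcomes are handled as in the primary analysis. Predictive value is judged by the interaction estimates with 95% confidence intervals for IV vs placebo, oral vs placebo and IV vs oral. This analysis is exploratory. Effects within high and low subgroups, including IV vs oral, are reported with 95% confidence intervals as descriptive results. Marker sample: [pre-operative or day 1]. Marker scale: [continuous, transformed if skewed, or a stated cut-off].

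The sponsor fills both brackets before unblinding. If the subgroups are unequal in size and their variances may differ, standard errors that allow for unequal variance should be named. If p-values are to support claims, a multiplicity rule across the 24 interaction contrasts is needed.

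The cost is wording only, since Annex 1 already schedules every sample. The real drawback is power: 29% to 35% for a 0.5 mmol/L difference in effect with a median split, and 23% to 28% with a 25/75 split. By the normal approximation, 80% power for that difference with a median split would need 8 × (0.7 × 2.80/0.5)² ≈ 123 to 124 per arm, about 372 in total. Moderate true differences will often be missed, and the report should say so.

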9.5 Alpha

We will employ an alpha of 5% (2-sided testing).

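### The marker analysis runs 48 subgroup tests at an unadjusted 5% with no lead hypothesis designated, so a false-positive predictive marker is far more likely than 5%

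*Combined protocol and SAP*

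**What the plan says.** Section 9.4 lists the markers: "These parameters are: CRP, transferrin, ferritin and hepcidin". Their significance is to be determined by "doing subgroup analyses among patients with either high or low values of the parameters", which the section explains as "i.e. the similar analyses as in 9.1 but within subgroups".

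Section 9.1 supplies the tests to be repeated: "Differences in change between the two experimental groups, and between each experimental group and the control group will be tested", by Student's t-test, on the change in hemoglobin from baseline to week 3 or week 6. Section 9.5 sets one error rate for all testing: "We will employ an alpha of 5% (2-sided testing".

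Section 2 has two secondary objectives on subgroups. One asks about patients "who have the greatest effect of the medication used (eg patients with low ferritin"; the other asks about patients "who respond better to ferinject than ferrous fumarate and vice versa (eg patients with elevated CRP". Both markers are introduced as examples.

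The documents give no cut-off for high and low, no treatment-by-marker test, no multiplicity adjustment, no order of priority among markers and no label of these analyses as exploratory. Annex 1 schedules all four markers before surgery and again on day 1 after it. Section 9.4 does not say which of the two samples defines high and low.

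**The concern.** Section 9.4 ties each marker's significance to several tests at 5%, and nothing limits how many of them may produce the finding. The more markers, subgroups, contrasts and weeks that are tested, the more likely it is that some marker appears predictive by chance alone.

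The result would be used. The introduction asks which women with anemia after caesarean section should receive iron, and whether blood values other than hemoglobin should inform that decision. A chance finding for one of four markers would look like an answer.

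The problem is separate from the form of the test. Comparing significance in the high subgroup with significance in the low subgroup is a weakness in itself. Replacing each pair with a direct test of the difference would cure that weakness and still leave 24 unadjusted tests.

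**Working it through.** **The plan's own figures.** The documents state no error rate for the marker analyses. The figure that can be reproduced is the sample size in section 4.4. With a difference of 0.5 mmol/L, SD 0.7, two-sided 5% and 80% power, the t-test solution is 31.76 per group, rounded up to 32. Three groups make 96, and 96 / (1 - 0.20) = 120. These agree with the plan, so 32 to 40 per arm is used below.

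**Number of tests.**
- As written: 4 markers (9.4) x 2 levels (9.4) x 3 contrasts (9.1) x 2 weeks (9.1) = 48.
- One subgroup-difference test per high/low pair: 4 x 3 x 2 = 24.
- One week only: 24 within-subgroup tests, or 12 difference tests.

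**Expected false positives with no true effect.** 48 x 0.05 = 2.4, and 24 x 0.05 = 1.2.

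**Chance of at least one.** If tests were independent this would be 1 - 0.95^48 = 91%, and 1 - 0.95^24 = 71%. Both are too high because the tests share patients. The chance was therefore simulated with no treatment effect, 1:1:1 allocation, median splits and pooled-variance t-tests. The correlation between week-3 and week-6 change was varied from 0 to 0.9, and the correlation between markers from 0 to 0.7. The documents give neither correlation and no cut-off, so these are assumptions.

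| Tests | Chance of at least one p < 0.05 |
|---|---|
| 48 within-subgroup, two weeks | about 58-78% |
| 24 subgroup-difference, two weeks | about 43-65% |
| 24 within-subgroup, one week | about 46-54% |
| 12 subgroup-difference, one week | about 32-43% |

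With 40 per arm, a week-3/week-6 correlation of 0.6 and uncorrelated markers, the two-week figures are about 72% and 60%. The lowest two-week figures come from correlations of 0.9 (weeks) and 0.7 (markers). Results with 32 per arm are similar.

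**Power inside a subgroup.** With 16 to 20 patients per arm in each half, power for 0.5 mmol/L is about 50-60%.

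**The proposed lead tests.** Two tests at 2.5% each hold the total false-positive risk to at most 2 x 2.5% = 5%.

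For power, assume SD 0.7, a normally distributed marker, an effect that varies linearly with it, and a difference of 0.5 mmol/L in treatment effect between marker halves. The means of the two halves of a normal variable lie 2 x 0.798 = 1.596 SD apart, so the interaction slope is 0.5 / 1.596 = 0.313 mmol/L per marker SD. Its standard error is √(2 x 0.7² / n), and the critical value at two-sided 2.5% is 2.241.
- n = 32 per arm: SE 0.175, ratio 1.79, power Φ(1.79 - 2.241) = about 33%.
- n = 40 per arm: SE 0.157, ratio 2.00, power Φ(2.00 - 2.241) = about 40%.

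**The case against.** The best defence is that these are secondary analyses, that section 1 says only that the markers may be of value in predicting the effect, and that formal error control for such questions is partly a matter of preference. Part of this stands: an exploratory label would meet much of the concern. But no such label appears, and 9.4 speaks of determining significance.

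A second defence is that 9.1 refers to either 3 or 6 weeks and 4.4 sizes the trial on week 3, so one week might be meant. Sections 2 and 7.1.1 name both weeks, so 48 is the fair count. The one-week figures are given because the wording leaves room for them.

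Third, the correlations are assumed. High values are plausible, because both changes share one baseline and section 9.6 carries the last hemoglobin value forward. At such values the difference-test figure falls below 50%. This stands, and it is why ranges are given.

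Fourth, part of the 58-78% belongs to the within-subgroup form of test. That also stands; the 43-65% isolates the number of tests.

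Some stronger readings are tempting but unsupported:
- A reader might infer that the plan has no marker hypotheses. It has two, offered as examples; none is designated as the lead.
- A reader might count 96 tests because there are two pre-treatment samples. The plan does not say that both will be used.
- A reader might infer that women would be selected for iron by marker. No section sets such a rule.

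**Conclusion.** The concern holds. As written, 9.4 allows 48 tests at an unadjusted 5%, with no lead hypothesis designated. With no true effect and median splits, the chance of at least one false-positive result is about 58-78%. Changing to subgroup-difference tests alone leaves about 43-65%. If one week is tested, the figures are about 46-54% and 32-43%.

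A reader might infer that a chance marker is more likely than not whatever is done. That is shown for the 48 tests in every setting tried. It is not shown for the difference tests at high correlations, nor for every one-week setting. The recommendation does not depend on it, since every figure is far above 5%. The point concerns a secondary objective and should be corrected before the analysis.

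**What to change.** Revise 9.4 in one paragraph, together with the change from within-subgroup tests to treatment-by-marker tests:

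- Name two lead interaction tests on week-3 hemoglobin, the time point used for the sample size, each at two-sided 2.5%.
- Test 1: ferritin with one stated 9.1 contrast, for example intravenous iron versus placebo. Pooled iron versus placebo is not a 9.1 contrast, and testing both iron arms would make three lead tests, so 2.5% each would no longer hold the total to 5%.
- Test 2: CRP with intravenous versus oral iron.
- Use each marker as a continuous value, log-transformed if skewed, so that no cut-off has to be chosen.
- Name in advance the one pre-treatment sample to be used, pre-operative or day 1.
- Report transferrin, hepcidin, the other contrasts and week 6 as interaction estimates with 95% confidence intervals, labelled hypothesis-generating.

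The cost is a short text change and no new data. There are two downsides. Transferrin and hepcidin cannot give a confirmed result. The lead tests have low power, roughly 33-40% under the assumptions shown, so 9.4 should state that a null result does not show absence of predictive value.
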